7.9.6 Definition and Duration of Neutrophil Recovery

Neutrophil recovery will be defined as an increase in absolute neutrophil count (ANC) to greater than $500/\mu L$ on two consecutive days.

Duration of neutrophil recovery will be defined as the difference between the date of transplant and the date of the first count above the threshold (i.e., $500/\mu$ L) of the two consecutive days.

Duration of Neutrophil Recovery =

(Date of first count above the threshold – Date of transplant) +1

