## 4.2.3 Treatment Visit-3 to Treatment Visit-11 (T11)

The following assessments will be performed at each visit, unless otherwise specified:

- Assess for any Adverse Events and changes in Concomitant medications (section 9 and 7.5),
- Diagnosis and Grading of GVHD (section 7.17 and 7.18)
- Physical examination (section 7.6) (at T8, T11)
- Vital Signs (section 7.9), (at T4, T6, T7, T8, T9, T10, T11)
- ECOG performance status (section 7.10) (at T4, T7, T9, T11)
- ECG (section 7.7) (at T6, T9, T11)
- Collection of Blood Specimens for:
  - o CBC w/diff (section 7.11.1)
  - o Serum biochemistry (section 7.11.2) (at T4, T6, T7, T8, T9, T10, T11)
  - Serum pregnancy test, for female subjects of childbearing potential (section 7.11.7) (at T7 and T11)
  - Anti-idiotypic antibodies to PRO 140 (section 7.11.6) (at T7 and T11)
  - Lymphocyte Phenotype Panel (section 7.11.4) (at T4, T6, T8 and T11)
  - o T-cell and myeloid chimerism (section 7.11.5) (at T6, T8 and T11)
- Collection of Urine Specimen for Urinalysis (section 7.11.8) (at T7 and T11)
- Study Treatment Administration (PRO 140 or Placebo) (section 7.13)
- Injection Site Reaction Assessment (section 7.15)

CONFIDENTIAL Page 61 of 108

Version 3.0 Date: 17 Jun 2016

- ➤ **Note:** To assess injection site reactions, refer to the investigator injection site reaction table (refer to section 17.1).
- Injection Site Pain Assessment (VAS) (section 7.16)

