#### 7.11 CLINICAL LABORATORY ASSESSMENTS

Blood and urine samples will be collected according to the time points in the schedule of assessments for analysis of the following parameters:

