#### 7.11.1 Routine CBC

- Includes hemoglobin, hematocrit (HCT), red blood cell (RBC) count, white blood cell (WBC) count, WBC differential count (%), absolute neutrophils count (ANC) and platelets count.
  - Note: Platelet recovery will be defined as post-transplant increase in platelet levels to greater than 20,000/µL on two consecutive counts at least 2 days apart, if no platelet transfusion is given on or between the days of the two counts and the second platelet count is at least as high as the first. The date of platelet recovery will be defined as the day of the first eligible count per above. Neutrophil

CONFIDENTIAL Page 73 of 108

recovery will be defined as an increase in absolute neutrophil count (ANC) to greater than  $500/\mu$ L on 2 consecutive days. The date of neutrophil recovery will be defined as the day of the first count above the threshold.

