8.2.2.4 Neutrophil and platelet count recovery

The number and percentages of subjects with neutrophil and platelet count recovery will be presented. The definition of neutophil and platelet count recovery is presented in Sections 7.9.5 and 7.9.6, respectively. Chi-square/ Fisher's exact test will be used to compare the incidence of neutrophil recovery and of platelet recovery between treatment groups.

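### Neutrophil recovery requires ANC above 500/µL on two consecutive days, but scheduled post-transplant blood counts are 7 to 14 days apart, so the endpoint cannot be reliably derived from the planned samples

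*SAP*

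**What the plan says.** **Definition.** SAP 7.9.6 reads: "Neutrophil recovery will be defined as an increase in absolute neutrophil count (ANC) to greater than" 500/µL "on two consecutive days". Protocol 7.11.1 has the same two-day condition and adds: "The date of neutrophil recovery will be defined as the day of the first count above the threshold". SAP 7.9.6 turns this into a duration in days from transplant.

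**Sampling.** Protocol 7.11 ties blood draws to the visit schedule: "Blood and urine samples will be collected according to the time points in the schedule of assessments". For T3 to T11, Protocol 4.2.3 says "The following assessments will be performed at each visit, unless otherwise specified", and its CBC item carries no visit restriction. Protocol Table 4-1 and SAP Appendix 1 therefore give one CBC on each of Days 0, 7, 14, 21, 28, 42, 56, 70, 84, 98 and 112. The window is ±3 days from Day 7 on. A CBC is also marked for unscheduled visits.

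**Analysis.** Neutrophil and platelet count recovery is a named secondary efficacy endpoint. SAP 8.2.2.4 states: "Chi-square/ Fisher's exact test will be used to compare the incidence of neutrophil recovery and of platelet recovery between treatment groups". SAP 7.3 rules out imputation.

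**The concern.** The definition is written for near-daily counts, while the schedule supplies weekly and then fortnightly ones. Taken together, the two leave the plan without a stated source for the second-day count that the definition needs.

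If only scheduled counts reach the database, most subjects will lack the pair of counts that would settle their status. The SAP does not say whether such a subject is missing or not recovered, so the reported percentage would depend on a programming choice made later. If some sites enter extra counts from the medical record and others do not, the percentage would partly measure data-entry practice. Either way, a prespecified between-arm comparison would say little about haematological recovery.

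Timing is also affected. Chimerism, the other planned engraftment measure, is first sampled at T6 (Day 28), so count recovery is the only engraftment-related endpoint with scheduled data before then.

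**Working it through.** The documents give no figure to reproduce. The check compares the definition with the spacing of the counts.

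**Inputs**
- Required spacing: 1 day (SAP 7.9.6; Protocol 7.11.1).
- Nominal CBC days: 0, 7, 14, 21, 28, 42, 56, 70, 84, 98, 112 (Protocol Table 4-1; SAP Appendix 1).
- Windows: none on Day 0; ±3 days at every later visit listed.
- 30 subjects per arm (SAP section 4).

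**Step 1: nominal gaps.** There are ten adjacent pairs: four gaps of 7 days (Day 0 to Day 28) and six of 14 days (Day 28 to Day 112). None of the ten is 1 day.

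**Step 2: smallest gap the windows allow.** Smallest gap = (later day − 3) − (earlier day + its window).

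| Pair | Smallest gap (days) |
|---|---|
| Day 0 / 7 | (7 − 3) − 0 = 4 |
| Days 7/14, 14/21, 21/28 | 7 − 3 − 3 = 1 |
| Each later pair | 14 − 3 − 3 = 8 |

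Only three pairs can fall on adjacent days, and each needs the earlier visit at +3 and the later one at −3.

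**Step 3: how often that happens.** The documents do not say how visits spread within their windows, so the range is shown.
- All visits on the nominal day: 0%.
- Visit days independent and uniform over the seven window days (assumption): each pair has probability 1/7 × 1/7 = 1/49. Neighbouring pairs exclude each other, because the shared visit cannot be at both −3 and +3. The Day 7/14 and Day 21/28 pairs can both occur, with probability 1/49 × 1/49 = 1/2401. So P(any pair) = 3/49 − 1/2401 = 146/2401 = 6.1%. Enumerating all 7⁴ = 2401 combinations of window offsets gives the same count.

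**Step 4: expected number.** 30 × 146/2401 = 1.8 subjects per arm, or 3.6 of 60 in the trial. Both counts must also exceed 500/µL, so the expected number who could be classed as recovered from scheduled counts is no higher than this.

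**Step 5: platelets for comparison.** The platelet rule (SAP 7.9.5) asks for consecutive counts at least 2 days apart. All ten nominal gaps meet that spacing.

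**The case against.** The case on the other side has several sound parts.

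- **More counts may exist.** Protocol 14.1 makes the medical record the primary source, with applicable data transcribed to the eCRF, and Protocol 7.19 keeps standard institutional transplant practice. The eCRF and Data Management Plan are not available here, so interim counts may in fact be captured. This stands as an unknown. It does not fill the gap, because neither the protocol nor the SAP says that such counts feed this endpoint. Unscheduled-visit CBCs are ad hoc.
- **Impossible to derive?** A reader might infer that the endpoint can never be derived. That is too strong: the windows, unscheduled visits and transcribed institutional counts can all yield adjacent-day pairs.
- **Nearly everyone a non-recoverer?** A reader might infer that almost every subject would be classed as not recovered. The documents do not say so. With no imputation under SAP 7.3, the status could equally be left missing.
- **A ceiling of 2 in 30?** The 1.8 is an expectation, not a maximum. Under the same model, the chance that three or more of 30 subjects have an adjacent-day pair is about 27%.
- **The main safeguard on engraftment?** Protocol 1.4.2 argues about stem-cell homing and does not mention count recovery. Donor chimerism is a separate secondary endpoint with its own failure definition (SAP 7.9.8) and test (SAP 8.2.2.3).
- **Platelets too?** The spacing problem does not carry over. Only the resolution of the platelet recovery date is coarse.
- **Limited stakes.** This is one of six listed secondary efficacy endpoints in a 60-subject proof-of-concept trial sized for descriptive results. Both blinded arms share the schedule, so the expected effect is lost information and not bias towards one arm. This stands, and it bears on severity.

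**Conclusion.** The point holds for neutrophil recovery. The two-day definition and the CBC schedule do not fit together, and the endpoint cannot be reliably derived from the planned samples. Scheduled counts supply an adjacent-day pair for 0% of subjects on nominal days and for about 6% under independent, uniform visit timing. That timing is an assumption with no support in the documents either way. The calculation excludes unscheduled-visit counts and any institutional counts that sites may enter.

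Even with the two-day condition relaxed, scheduled counts would date recovery only to within about 7 days up to Day 28 and about 14 days afterwards. This matters less for the planned test, because SAP 8.2.2.4 compares proportions. The durations in SAP 7.9.6 have no dedicated analysis beyond the general Kaplan-Meier statement in SAP 8.1.

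This is a should-fix for a secondary endpoint. The primary endpoint is unaffected.

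**What to change.** Choose one of two routes and settle it before unblinding, so that the rule is not chosen with the results in view.

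**(a) Collect the counts.** State in Protocol 7.11.1 and the schedule that every dated institutional ANC from Day 0 until the recovery definition is met is entered in the eCRF. Derive SAP 7.9.6 from those records. The cost is modest extra data entry. It assumes that transplant units already take these counts for routine care; on that assumption there is no added blood draw or procedure. Entering platelet counts alongside would sharpen the platelet recovery date, but is optional.

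**(b) Fit the definition to the schedule.** If only scheduled CBCs will be used, redefine recovery in Protocol 7.11.1 and SAP 7.9.6 as two consecutive available counts above 500/µL, and report it as recovered by visit (Day 14, 21, 28). Say whether the visit is that of the first or the second count. If it is the first, as now, recovery at Day 28 needs the Day 42 count to confirm it. The cost is coarser timing.

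Under either route, SAP 8.2.2.4 should say how a subject without a qualifying second count is classified and which denominator is used. The same section should also correct its cross-reference: it cites 7.9.5 and 7.9.6 for neutrophils and platelets in that order, but 7.9.5 is the platelet definition and 7.9.6 the neutrophil one.

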7.9.7 Duration of GVHD-Free Survival (GFS)

GFS is defined as the duration from the day of transplant (Day 0/T2) until GVHD related death. Survivors, lost to follow-up and non-GVHD death are censored.

[for those with GVHD related death]

Days to event = (Date of death - Date of transplant) + 1

[for those who completed the study]

Days to censoring = (Date of completion – Date of transplant) +1

[for those who lost to follow-up]

Days to censoring = (Date of last response assessment – Date of transplant) +1

[for those with non-GVHD related death]

Days to censoring = (Date of death – Date of transplant) +1

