## 8.2.2 Secondary Efficacy Endpoints

- Incidence of severe and life-threatening (Grade III and Grade IV) acute GVHD by Day 100
- Incidence of organ-specific acute GVHD by Day-100
- Effect of PRO 140 or Placebo on donor engraftment by T-cell and myeloid chimerism in peripheral blood
- Effect of PRO 140 or Placebo on neutrophil and platelet count recovery
- Changes in ECOG performance score
- GVHD-free survival (GFS)

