### 9.1.6 Outcome Assessment

The outcome of the event will be assessed as either: resolved, resolved with sequelae, ongoing, or death. Only one AE per subject is allowed to have an outcome assessment as "death." If there are multiple causes of death for a given subject, only the primary cause of death will have an outcome of death.

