4. SAMPLE SIZE DETERMINATION AND RATIONALE, STATISTICAL POWER, AND SIGNIFICANCE LEVEL

For this two arm clinical trial, it is planned to have a total of 60 subjects (30 per treatment group). This is a proof of concept study, and sample size is on the basis of clinical judgment and not based on statistical power calculation. The number of subjects was deemed adequate to provide clinically meaningful descriptive results consistent with study objectives. Based on literature review, the incidence of GVHD in ablative transplant population range from 40-60%. Assuming that the control incidence of GVHD is 50% and that of the Active group is 15%, a sample size of 30 subjects per group produces a two-sided 95% CI for the difference in proportions with a width of 0.44 (i.e.,95% CI of 0.13 – 0.57).

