8.2.2.6 GVHD-free survival (GFS)

GFS will be defined as the elapsed time between the date of transplant until GVHD related death. Duration of GVHD-free survival will be measured as in Section 7.9.7.

GVHD-free survival will be compared between the treatment groups using Log-rank test and Kaplan-Meier methods will be used to depict the survival curves.

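### SAP 'GVHD-free survival' counts only GVHD-related death, so it measures cause-specific GVHD mortality under the wrong name and without a common time horizon

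*SAP*

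**What the plan says.** The protocol lists GVHD-free survival (GFS) among the secondary efficacy endpoints in the synopsis, section 2 and section 8.2.2. It defines the endpoint in none of them.

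The SAP supplies the definition twice, in the same terms:

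- Section 7.9.7: "GFS is defined as the duration from the day of transplant (Day 0/T2) until GVHD related death". On censoring: "Survivors, lost to follow-up and non-GVHD death are censored". A formula follows for each of four outcomes: GVHD-related death, completion, loss to follow-up and non-GVHD death.
- Section 8.2.2.6: "GFS will be defined as the elapsed time between the date of transplant until GVHD related death". On analysis: "GVHD-free survival will be compared between the treatment groups using Log-rank test", and "Kaplan-Meier methods will be used to depict the survival curves".

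Neither section makes the onset of GVHD, at any grade, an event, and neither says how a death is judged to be GVHD-related. The nearest rule is in protocol 9.1.6, on adverse event outcomes: "If there are multiple causes of death for a given subject, only the primary cause of death will have an outcome of death".

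On timing, protocol 5.1 treats a subject as having completed the study after the 14-week Treatment Phase and the 2-week follow-up. The Schedule of Assessments puts that visit at Day 112 ± 3. Protocol section 4 and SAP 2.3 continue follow-up to one year after the first treatment visit.

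**The concern.** The label and the quantity disagree in both halves of the name. A subject alive with Grade IV GVHD is still counted as event-free, so the curve does not show freedom from GVHD. A subject who dies of relapse, infection or toxicity is censored, so the curve does not show survival either.

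GFS is a named secondary efficacy endpoint and the only one with a planned log-rank comparison. A reader of a clinical study report would take a GVHD-free survival curve as the proportion alive without GVHD. That reader could be misled in either direction. The curve could look favourable in an arm where GVHD was frequent, or show no difference because few subjects died of GVHD although onset was prevented.

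**Working it through.** **Inputs from the documents.** SAP section 4: "Assuming that the control incidence of GVHD is 50% and that of the Active group is 15" per cent, with 30 subjects per arm. These rates give the SAP's own precision figure: 0.35 ± 1.96 × √(0.50×0.50/30 + 0.15×0.85/30) = 0.35 ± 0.220, or 0.13 to 0.57, width 0.44, as printed. That figure concerns the primary endpoint. The SAP gives no planning figure for GFS.

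**Assumed inputs.** The documents do not say what share *f* of GVHD cases die of GVHD, so *f* is taken as 10–50%, equal in both arms. Protocol section 1.2 says transplantation-related mortality can reach 20–30%. The figures for other deaths and one-year mortality used below are assumptions, not document values.

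**1. What is left out.** Expected onsets are 30 × 0.50 + 30 × 0.15 = 15 + 4.5 = 19.5 of 60. Before any deaths, 15/30 = 50% of control and 25.5/30 = 85% of active subjects stay free of GVHD.

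**2. What is counted.** Expected events are 19.5*f*. The curves end at 1 − 0.50*f* (control) and 1 − 0.15*f* (active).

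| *f* (assumed) | Events | Control | Active | Gap |
|---|---|---|---|---|
| 0.10 | 1.95 | 95% | 98.5% | 3.5 points |
| 0.50 | 9.75 | 75% | 92.5% | 17.5 points |

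**3. Kaplan-Meier with competing deaths censored.** Let *g* be the true proportion dying of GVHD and *o* the proportion dying of other causes, with proportional cause-specific hazards. Then 1 − KM = 1 − (1 − *g* − *o*)^(*g*/(*g* + *o*)).

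- *g* = 0.10, *o* = 0.20: 1 − 0.70^(1/3) = 0.112.
- *g* = 0.10, *o* = 0.30: 1 − 0.60^(1/4) = 0.120.

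The overstatement is 1.2 to 2.0 points on a true 10%.

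**4. Horizon.** A living completer is censored near Day 112. The event formula uses the date of death with no end date, and adverse events are still assessed at the one-year visit. A subject who completes and later dies of GVHD therefore fits two of the formulas in SAP 7.9.7. If the completion formula is applied, the death is dropped. If the death formula is applied, the only subjects still at risk after the last completion date are those who later die. With *k* late GVHD deaths and nobody else at risk, the Kaplan-Meier factors are (*k* − 1)/*k* × … × 0/1 = 0, so the curve reaches zero however small *k* is.

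**5. Overlap if GFS is instead redefined as onset or any death by Day 100.** Assume one-year mortality of 20% or 30%, a constant hazard, and independence from onset.

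- Death by Day 100 is 1 − 0.80^(100/365) = 5.9%, or 1 − 0.70^(100/365) = 9.3%.
- Event-free proportions are 0.50 × 0.941 = 47.0% and 0.85 × 0.941 = 80.0%, or 0.50 × 0.907 = 45.3% and 0.85 × 0.907 = 77.1%.
- Events are 30 × (0.530 + 0.200) = 21.9, or 30 × (0.547 + 0.229) = 23.3.

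Up to 19.5 of these, or 84–89%, are onsets already counted in the primary endpoint.

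**The case against.** The two SAP sections agree with each other and give formulas, so the endpoint is not internally contradictory. Onset is tested in the primary endpoint and in the Grade III–IV and organ-specific endpoints. Deaths from other causes appear in the serious adverse event summaries, and relapse is reported by arm. The trial is an unpowered proof of concept. All of this stands, and it limits the harm to one mislabelled secondary result.

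Four stronger readings are tempting, and the documents do not support them:

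- *The log-rank test is invalid.* It is not. With non-GVHD deaths censored, it compares the cause-specific hazards of GVHD death. Only reading the Kaplan-Meier complement as an incidence is off, and modestly so.
- *The gap between 35 points and 3.5–17.5 points is an error.* It is not. The two are different quantities, and the second depends on an assumed fatality share. The comparison shows how far the label could mislead, not a bias in an estimate.
- *Protocol 5.1 contradicts the one-year follow-up over when a subject completes.* It does not. Section 5.1 is the only definition of completion, whereas section 4 and SAP 2.3 describe length of follow-up. What remains is that events and censoring have no common end.
- *A composite of onset and death is the only acceptable repair.* It is not. That composite largely repeats the primary endpoint, as step 5 shows. Taking acute GVHD to the Day 112 visit would also cross the Day-100 limit used for the protocol's incidence endpoints and its own boundary with chronic GVHD in section 1.2.

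**Conclusion.** The point holds as a labelling and specification fault in a secondary efficacy endpoint. Followed exactly, SAP 7.9.7 and 8.2.2.6 report cause-specific GVHD mortality under the name GVHD-free survival, and no protocol text corrects this. That conclusion comes from the definitions and needs no assumption.

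The sizes are illustrations. The 19.5 uncounted onsets follow from the SAP's planning rates. The 1.95–9.75 events depend on the assumed 10–50% fatality, and the 11.2–12.0% depends on assumed death rates with proportional hazards. The missing common horizon is real, but its effect depends on how late deaths are programmed, which the SAP does not say. It should be corrected before unblinding. The primary analysis is unaffected.

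**What to change.** **Main change, in SAP 7.9.7 and 8.2.2.6:**

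- Rename the endpoint GVHD-related mortality.
- State before unblinding how a death is attributed to GVHD. The primary cause of death under protocol 9.1.6 is one available basis. It may be narrower than GVHD-related: an infection death during GVHD could have infection as its primary cause. The SAP should say which meaning is intended.
- Show cumulative incidence with other deaths as a competing event. The log-rank test can stay, described as a comparison of cause-specific hazards.
- Set one stated horizon for both events and censoring, and add a censoring rule for living subjects who withdraw, for whom 7.9.7 has no formula.

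**Alternative, if the name GFS is kept:** define the event as the first of Grade II–IV acute GVHD or death from any cause, with administrative censoring at Day 100 to match the primary endpoint. Censor withdrawals at their last GVHD grading and do not count deaths after withdrawal. Otherwise withdrawn subjects who die become events while those who live are censored early, which pulls the curve down.

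**Cost.** SAP wording and programming only. GVHD gradings, deaths and primary cause of death are already collected. Renaming alone is the smallest step and removes the misreading. The alternative adds little beyond the primary endpoint, because most of its events are already counted there.

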7.9.8 Donor Engraftment Failure

Donor engraftment failure is defined as T-cell or myeloid has, or both have less than 5% chimerism from the donor at anytime in the study duration after transplant.

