#### 4.3 FOLLOW-UP PHASE

## 4.3.1 Follow-Up Visit 1

The follow-up visit 1 will occur two (2) weeks after the last treatment visit. The following assessments will be performed at the follow-up visit 1, unless otherwise specified:

- Assess for any Adverse Events and changes in Concomitant medications (section 9 and 7.5),
- Vital Signs (section 7.9),
- ECOG performance status (section 7.10)
- Collection of Blood Specimens for
  - o CBC w/diff (section 7.11.1)
  - o Serum biochemistry (section 7.11.2)
- ECG (section 7.7)
- Grading GVHD skin, gut, liver (section 7.17)

### 4.3.2 Follow-up Visit 2

The follow-up visit 2 will occur one year after the first treatment visit. The following assessments will be performed at the follow-up visit 2, unless otherwise specified:

- Assess for any Adverse Events and changes in Concomitant medications (section 9 and 7.5),
- Vital Signs (section 7.7),
- Collection of Blood Specimens for:
  - o T-cell and myeloid chimerism (section 7.11.5).

CONFIDENTIAL Page 62 of 108

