### 5 SUBJECT COMPLETION AND WITHDRAWAL

#### 5.1 SUBJECT COMPLETION

A subject who completes the 14-week Treatment Phase and 2-week Follow-Up Phase will be considered as having completed the study.

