# 9.1.10 Study Stopping Rules

Upon occurrence of any of the following events, data will be reviewed by the Data Monitoring Committee (DMC):

- 1. Occurrence of a Grade 4 toxicity or two (2) occurrences of Grade 3 toxicities that are assessed to be definitely, probably or possibly study drug-related by the treating investigator;
- 2. Occurrence of more than 20 percent mortality by day +100;
- 3. Occurrence of more than 5 percent graft failures by day +100;
- 4. Occurrence of 5 or more of the first 10 subjects experiencing acute Grade II-IV GVHD.

CONFIDENTIAL Page 89 of 108

Version 3.0 Date: 17 Jun 2016

The DMC will make a recommendation to the study investigators, who, in consultation with the sponsor will decide whether to stop enrollment in the study.

[figure not shown]

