2.3 Study Duration

A subject will be in this trial at maximum of around 56 weeks.

- **Screening Phase:** up to 4 weeks (28 days).
- Treatment Phase: up to 14 weeks \pm allowed windows (up to 14 treatments).
- Follow-up Phase: up to one year after first treatment visit (T1), approx. 38 weeks from end of treatment visit].

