8.2.2.3 Donor engraftment evaluated by T-cell and myeloid chimerism in peripheral blood

The number and percentages of subjects with donor engraftment failure evaluated by T-cell and myeloid chimerism in peripheral blood will be presented by different treatment groups. The definition of donor engraftment failure is presented in Section 7.9.8. Chi-square/ Fisher's exact test will be used to compare the incidence of donor engraftment failure.

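### SAP 7.9.8 recognises donor engraftment failure only through a chimerism result below 5%, so unsampled early deaths cannot count, relapse can, and no specific analysis of percent chimerism is named

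*SAP*

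**What the plan says.** - **Definition.** SAP 7.9.8 calls it donor engraftment failure when the T-cell lineage, the myeloid lineage or both show "less than 5% chimerism from the donor at anytime in the study duration after transplant". Count recovery, death, relapse and a closing date play no part.
- **Sampling.** Protocol 4.2.3 lists "T-cell and myeloid chimerism (section 7.11.5) (at T6, T8 and T11"), which the schedule of assessments places at Days 28, 56 and 98, each ±3 days. The last sample is at Follow-up Visit 2 (Day 365±14): "The follow-up visit 2 will occur one year after the first treatment visit". The schedule marks none earlier and none at unscheduled visits.
- **Analysis.** SAP 8.2.2.3 reports the "number and percentages of subjects with donor engraftment failure evaluated by T-cell and myeloid chimerism" and says that a Chi-square or Fisher's "exact test will be used to compare the incidence of donor engraftment failure". SAP 8.1, and protocol 8.7.5.1 for secondary endpoints, provide a t-test or non-parametric method for continuous data in general.
- **Missing data.** SAP 7.3 allows no imputation. Protocol 8.6.4 promises imputation for the ITT population, with methods to be given in the SAP.
- **Related items.** Neutrophil and platelet recovery are compared in SAP 8.2.2.4. Relapse by Day 100 is a safety endpoint (SAP 3.1.3). Protocol 9.1.9 names graft failure and relapse as two distinct events. Protocol 9.1.10 sends the data to the DMC on "Occurrence of more than 5 percent graft failures by day +100", without defining graft failure.

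**The concern.** Protocol 1.4.2 argues that CCR5 blockade should not interfere with stem-cell homing. The engraftment endpoint tests that directly, so its definition should separate graft loss from other events. Followed literally, SAP 7.9.8 has three weaknesses.

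1. A subject who dies or leaves before the first chimerism visit has no value below 5%. Counted in the denominator, that subject becomes a silent success; dropped, the analysis is no longer ITT. The SAP does not choose.
2. Host myeloid cells that return with leukaemic relapse meet the definition. If relapse differs between arms, the difference appears as an engraftment effect. If it does not, a real difference is diluted.
3. The one named analysis is of a probably rare dichotomy. The lineage-specific percentages from three on-treatment visits have no stated visit, lineage or handling of deaths.

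**Working it through.** **The plan's own figure.** No rate or precision is stated for engraftment failure. The only design figure, in SAP section 4, concerns GVHD at 50% v 15% with 30 per arm. It reproduces: 0.35 ± 1.96 × √(0.5×0.5/30 + 0.15×0.85/30) = 0.35 ± 0.22, or 0.13 to 0.57, width 0.44. It has no bearing on this endpoint.

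**Who can be a failure.** The first sample falls at Day 28 − 3 = Day 25 at the earliest.
- Alive and sampled with <5% in either lineage: failure.
- Died or left before any sample: never a failure, denominator unstated.
- Counts never recover but donor cells are ≥5%: not a failure here; seen in SAP 8.2.2.4.
- Relapse followed by <5% donor cells: failure. Protocol 5.2.1 continues follow-up after study treatment stops, so such samples can arise.

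**Time limit.** SAP 2.3 says "A subject will be in this trial at maximum of around 56 weeks", which includes Day 365. Protocol 5.1 says "A subject who completes the 14-week Treatment Phase and 2-week Follow-Up Phase will be considered as having completed the study", which ends near Day 112 (98 + 14). The one-year reading is the natural one, because chimerism is scheduled at Day 365, but the wording does not settle it.

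**Unclassifiable subjects.** The documents give no early-death rate. Assume probability d of death before Day 25. The expected number per arm is 30d, and the chance of at least one among 60 is 1 − (1 − d)^60.

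| d (assumed) | Per arm | At least one in 60 |
|---|---|---|
| 2% | 0.6 | 70% |
| 5% | 1.5 | 95% |
| 10% | 3.0 | 99.8% |

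**Sensitivity of the dichotomy.** Use 30 v 30 and a two-sided level of 0.05 (protocol 8.7 prints 0.05%; I read it as 0.05). With all k failures in one arm, Fisher's p = 2 × C(30,k)/C(60,k).
- k = 5: 2 × 142,506/5,461,512 = 0.052.
- k = 6: 2 × 593,775/50,063,860 = 0.024.

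So 0 v 6 is the smallest significant split from zero. Exact power, summing the two binomial probabilities over all tables with p < 0.05, is 9% for 5% v 15% and 24% for 5% v 20%. All these rates are assumptions.

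**Effect of misclassification.** Let s be the share of true failures captured and r the share of the remaining subjects counted through relapse, equal in both arms. The observed rate is p·s + (1 − p)·r. For true rates of 5% v 20%:

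| s | r | Observed rates | Power |
|---|---|---|---|
| 1 | 0 | 5.0% v 20.0% | 24% |
| 0.75 | 0 | 3.75% v 15.0% | 12% |
| 1 | 0.10 | 14.5% v 28.0% | 16% |
| 0.75 | 0.10 | 13.25% v 23.0% | 9% |

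**DMC trigger.** With 60 subjects, 3/60 is exactly 5% and 4/60 = 6.7%, so the fourth graft failure crosses the line. If the trigger borrows the SAP definition, one misclassified subject could decide it.

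**The case against.** There are several good points on the plan's side.

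- A reader might infer that primary graft failures are not counted at all. The documents do not support that. A subject with primary failure who is sampled with <5% donor cells in either lineage meets the definition, and failed neutrophil recovery is compared separately in SAP 8.2.2.4.
- A reader might infer that the chimerism percentages are never compared. SAP 8.1 and protocol 8.7.5.1 cover continuous data generally. What is missing is a named analysis.
- A reader might take 5% as the expected graft-failure rate. It is a threshold for DMC review.
- The day +100 limit in protocol 9.1.10 belongs to a monitoring trigger. The engraftment endpoint was never limited to Day 100, so the differing horizons are not in themselves an error.
- The sample size is expressly not power-based, so low power for a rare secondary event is no defect. The first two power figures show only how insensitive the dichotomy is; they do not measure misclassification.

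All of this stands, and it narrows the point. It does not answer the unsampled early deaths, the unstated denominator or the relapse-driven failures. Neutrophil recovery is only a partial backstop: SAP 7.9.6 sets no deadline and needs counts on two consecutive days, whereas scheduled blood counts are weekly to Day 28 and two-weekly to Day 112.

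**Conclusion.** The concern holds in limited form. SAP 7.9.8, applied as written, cannot register subjects who die or leave before the first chimerism visit, leaves their place in the denominator open, and counts loss of donor cells after relapse as engraftment failure. SAP 8.2.2.3 names only the dichotomy and leaves percent donor chimerism to a generic rule.

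The size cannot be fixed from the documents, which give no graft-failure, early-death or relapse rates. Under the assumptions above, 0.6 to 3.0 subjects per arm would be unclassifiable. Imperfect capture and relapse counts together could cut power from 24% to 9% in the 5% v 20% case. The endpoint is secondary, but it bears on a safety question that the protocol itself discusses, and the wording should be corrected before database lock.

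**What to change.** **SAP 7.9.8**
- Count donor chimerism <5% in either lineage by the Day 98 visit and before any documented relapse.
- Show as separate categories subjects with <5% after relapse, deaths before the first chimerism visit, and other subjects with no sample. State the ITT denominator.
- Report Day 365 separately.
- Cross-tabulate with neutrophil recovery from SAP 8.2.2.4. Do not add a new count-recovery cut-off: the documents contain none, and consecutive-day counts are not on the visit schedule.

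**SAP 8.2.2.3**
- Add a Wilcoxon comparison, with medians, of percent donor T-cell and percent donor myeloid chimerism at Days 28, 56 and 98 among assessed subjects.

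**Protocol 9.1.10**
- State whether the graft-failure trigger uses the SAP definition, and reconcile the two passages.

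**Cost.** SAP wording and one more table; the chimerism samples are already scheduled. Relapse dates must be available. Relapse by Day 100 is already a safety endpoint, but the schedule of assessments has no row for it, so confirm that the dates are captured.
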